4.3 Withdrawal of Subjects from Study Treatment and/or Study

Permanent discontinuation of investigational product

An individual subject will not receive any further investigational product if any of the following occur in the subject in question:

1. Withdrawal of consent or lost to follow-up.

2. Adverse event that, in the opinion of the investigator or the sponsor, contraindicates further dosing.
3. Subject is determined to have met one or more of the exclusion criteria for study participation at study entry and continuing investigational therapy might constitute a safety risk.
4. Pregnancy or intent to become pregnant.
5. Any AE that meets criteria for discontinuation as defined in Appendix 1, Section 10.1.3
6. Adverse event related to durvalumab of any Grade>3 ADRs or repetitive Grade 3 ADRs with the exception of toxicities that do not meet the criteria for discontinuation as defined in Section 10.1.3, Appendix 1
7. Grade ≥ 3 infusion reaction.
8. Subject non-compliance that, in the opinion of the investigator or sponsor, warrants withdrawal; eg, refusal to adhere to scheduled visits.
9. Initiation of alternative anticancer therapy including another investigational agent.
10. Confirmation of PD and investigator determination that the subject is no longer benefiting from treatment with durvalumab.

Subjects who are permanently discontinued from further receipt of investigational product, regardless of the reason (withdrawal of consent, due to an AE, other), will be identified as having permanently discontinued treatment.

Subjects who are permanently discontinued from receiving investigational product will be followed for [REDACTED]

[REDACTED], unless consent is withdrawn or the subject is lost to follow-up or enrolled in another clinical study. All subjects will be followed for survival. Subjects who decline to return to the site for evaluations will be offered follow-up by phone every 3 months as an alternative.

Withdrawal of consent

Clinical Study Protocol

Drug Substance Durvalumab (Medi4736)

Sponsor code: GECP 16/04

Version Number 4.1

Date 14th November 2018

If consent is withdrawn, the subject will not receive any further investigational product or further study observation.

4.4 Replacement of subjects

Subjects withdrawn from the study will not be replaced.

5. INVESTIGATIONAL PRODUCT(S)

5.1 Durvalumab

The sponsor will supply durvalumab to the site's pharmacies as a 500-mg vial solution for infusion after dilution.

5.1.1 Formulation/packaging/storage

Durvalumab will be supplied by AstraZeneca as a 500-mg vial solution for infusion after dilution. The solution contains 50 mg/mL durvalumab, 26 mM histidine/histidine-hydrochloride, 275 mM trehalose dihydrate, and 0.02% (weight/volume) polysorbate 80; it has a pH of 6.0. The nominal fill volume is 10 mL. Investigational product vials are stored at 2°C to 8°C (36°F to 46°F) and must not be frozen. Durvalumab must be used within the individually assigned expiry date on the label.

The trial medication and its packaging will be labeled in accordance with annex 13 of EU Guidelines to Good Manufacturing Practice.

Term	Percentage
GMOs	~55%
Organic	~95%
Natural	~95%
Artificial	~35%
Organic	~95%
Natural	~95%
Artificial	~35%
Organic	~95%
Natural	~95%
Artificial	~35%

Clinical Study Protocol

Drug Substance Durvalumab (Medi4736)

Sponsor code: GECP 16/04

Version Number 4.1

Date 14th November 2018

[REDACTED]

Clinical Study Protocol

Drug Substance Durvalumab (Medi4736)

Sponsor code: GECP 16/04 [REDACTED]

Version Number 4.1

Date 14th November 2018

[REDACTED]

[REDACTED]

[REDACTED]

[REDACTED]

[REDACTED]

[REDACTED]

[REDACTED]

[REDACTED]

[REDACTED]	[REDACTED]
[REDACTED]	[REDACTED]
[REDACTED]	[REDACTED]

[REDACTED]

5.1.5 Accountability and dispensation

The investigator is responsible for ensuring accountability for trial drug, including reconciliation of drugs and maintenance of drug records.

[REDACTED]

Clinical Study Protocol

Drug Substance Durvalumab (Medi4736)

Sponsor code: GECP 16/04

Version Number 4.1

Date 14th November 2018

A horizontal bar chart illustrating the percentage of respondents who have heard of various topics. The y-axis lists the topics, and the x-axis represents the percentage, ranging from 0% to 100% in increments of 10%. The bars are black and set against a white background.

Topic	Percentage
Healthcare	98%
Technology	95%
Finance	92%
Politics	88%
Entertainment	85%
Science	82%
Food	78%
Sports	75%
Business	72%
Art	68%
History	65%
Geography	62%
Mathematics	58%
Chemistry	55%
Physics	52%
Biology	48%
Spanish	45%
French	42%
German	38%
Japanese	35%
Korean	32%
Chinese	28%
Arabic	25%
Russian	22%
Swahili	18%
Portuguese	15%
Urdu	12%
Hindi	10%
Malay	8%
Turkish	5%
Polish	3%
Swedish	2%
French Canadian	1%
Other	1%

6. TREATMENT PLAN

6.1 Subject enrollment

Only persons meeting all inclusion criteria and no exclusion criteria may be enrolled into the trial as subjects. Prior to performing any trial assessments not part of the subject's routine medical care, the investigator will ensure that the subject or his/her legal representative, has provided written informed consent following the procedure.

6.1.1 Procedures for handling subjects incorrectly enrolled

Subjects who are incorrectly enrolled or initiated on treatment should be withdrawn from the study.

Clinical Study Protocol

Drug Substance Durvalumab (Medi4736)

Sponsor code: GECP 16/04

Version Number 4.1

Date 14th November 2018

Clinical Study Protocol

Drug Substance Durvalumab (Medi4736)

Sponsor code: GECP 16/04

Version Number 4.1

Date 14th November 2018

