Institution's name and place: _____

Signature

Date

Clinical Study Protocol

Drug Substance Durvalumab (Medi4736)

Sponsor code: GECP 16/04_ [REDACTED]

Version Number 4.1

Date 14th November 2018

Investigational Drug Substance(s)	Durvalumab (Medi4736)
Version	4.1
Date	14 th November 2018

A phase II exploratory study of durvalumab (MEDI4736) in HIV-1 patients with advanced solid tumors

Sponsor: Fundación GECP
[name]
[name]
[contact] / [contact]
E-mail: [contact]

Principal Investigator: [REDACTED]
Instituto Oncológico [name]
Oncology Department
[name]
[name]
[REDACTED]
[REDACTED]

Study Coordinator: [REDACTED]
Instituto Oncológico [name]
Oncology Department
[name]
[name]
[REDACTED]
[REDACTED]

PROTOCOL SYNOPSIS

Clinical Protocol GECP16/04 (ESR 15-10869)

Study Title:Phase II exploratory study of durvalumab (MEDI4736) in HIV-1 patients with advanced solid tumors

Protocol Number: GECP 16/04 [REDACTED]

Clinical Phase: II

Study Duration: Recruitment period will be 12 months First subject in: Q1, 2016 Last subject out: Q1, 2018 Survival follow-up will continue until 5 years after the last subject receives the last dose of durvalumab

Investigational Product(s) and Reference Therapy: Durvalumab will be supplied in glass vials containing 500 mg of liquid solution at a concentration of 50 mg/mL for intravenous (IV) administration.

Research Hypothesis PD-1/ PD-L1 coinhibitory pathway plays a significant role in the regulation of the immune response in both chronic infectious diseases and cancer. Preclinical and animal data support the safety and promising activity of anti-PD-1 antibody in HIV-1 infection. Demonstrated anticancer activity and safety profile of durvalumab (MEDI4736) in cancer clinical trials. Unlikely drug interactions of durvalumab (MEDI4736) and antiretroviral treatments. We propose a phase II clinical study designed to assess the feasibility of durvalumab (MEDI4736) in HIV-1-infected individuals with solid tumors. Additionally we hope to obtain data that let us understand

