2.2 Secondary objective(s)

- To assess ORR (RECIST 1.1 and irRECIST) and duration of response

Clinical Study Protocol

Drug Substance Durvalumab (Medi4736)

Sponsor code: GECP 16/04_ [REDACTED]

Version Number 4.1

Date 14th November 2018

- To evaluate the PFS rate at 6 months
- To evaluate the OS rate at 12 months

Durvalumab (MEDI4736) has demonstrated activity in several cancer types in the general population. In this study, as secondary objective, we will analyze activity of the drug as activity in terms of Response rate according to RECIST1.1 criteria, and according to OS rate at 12 months and PFS at 6 months.

Several data indicate that anti PD-1/PD-L1 treatments in oncology could have activity in terms of OS with long responders, that it is not always correlated to classical endpoint of response rate or median survival.

In this trial given that patients will be included with different solid tumors, and different lines of treatment, activity of the drug is a secondary objective, in order to determine if activity looks similar to activity reported in solid tumors without HIV- infection.

Clinical Study Protocol

Drug Substance Durvalumab (Medi4736)

Sponsor code: GECP 16/04_

Version Number 4.1

Date 14th November 2018

Clinical Study Protocol

Drug Substance Durvalumab (Medi4736)

Sponsor code: GECP 16/04_ [REDACTED]

Version Number 4.1

Date 14th November 2018

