11. STATISTICAL METHODS AND SAMPLE SIZE DETERMINATION

11.1 Description of analysis sets

The screening analysis set includes all subjects who signed the ICF.

ITT Analysis set: the ITT analysis set will include all subjects who were included into the trials.

Per-protocol analysis set will include all ITT subjects who do not have major protocol violations.

[REDACTED]

[REDACTED]

[REDACTED]

[REDACTED]

[REDACTED]

[REDACTED]

[REDACTED]

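### Section 6.1.1 withdraws incorrectly enrolled patients from the study even after dosing, whereas 4.3 follows all subjects for survival; read literally, 12-month OS is lost for patients who stay in ITT (minor)

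*Combined protocol and SAP*

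**What the plan says.** Section 6.1.1, on subjects enrolled in error, gives one visible rule: "Subjects who are incorrectly enrolled or initiated on treatment should be withdrawn from the study". It does not separate errors found before the first dose from errors found after it.

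Section 4.3 keeps stopping drug apart from ending observation.

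- Item 3 of its list of reasons to stop durvalumab covers a subject found to have met "exclusion criteria for study participation at study entry and continuing investigational therapy might constitute a safety risk".
- Follow-up after stopping drug applies "unless consent is withdrawn or the subject is lost to follow-up or enrolled in another clinical study". What that follow-up consists of is blacked out.
- The next sentence is visible in full: "All subjects will be followed for survival".
- Only withdrawn consent is said to end observation: "If consent is withdrawn, the subject will not receive any further investigational product or further study observation".

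The synopsis adds: "Survival follow-up will continue until 5 years after the last subject receives the last dose of durvalumab". Section 4.4 rules out replacing withdrawn subjects. Section 11.1 states that "the ITT analysis set will include all subjects who were included into the trials". One of the secondary objectives in 2.2 is "To evaluate the OS rate at 12 months"; another is the 6-month PFS rate.

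**The concern.** A site that finds an eligibility error in a treated patient would turn first to 6.1.1, which is headed for that situation and tells it to take the patient out of the study. Section 4.3 tells the same site to keep following everyone for survival. Different centres may settle this differently.

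Where 6.1.1 is followed as written, the patient remains in ITT but contributes no survival information after withdrawal. The loss then comes from a rule, and the rule selects on eligibility. Several entry criteria in 4.1 track prognosis: ECOG 0-2, life expectancy of at least 16 weeks, and adequate organ and marrow function. A patient withdrawn for failing one of these may have a different survival outlook from the patients who remain, so treating the withdrawal as non-informative censoring could bias the Kaplan-Meier estimate.

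**Working it through.** **Comparison of the texts for a dosed patient found ineligible**

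- Drug: 6.1.1 implies stopping. Section 4.3 item 3 requires stopping if there is a safety risk. The 4.3 list is not stated to be exhaustive, so stopping drug under 6.1.1 is not in itself a contradiction.
- Survival follow-up: 6.1.1 ends study participation. Section 4.3 continues survival follow-up for all subjects, and ineligibility is not among its visible exceptions. The conflict lies here.
- Tumour follow-up: the 4.3 clause is blacked out. Section 10.3.1 takes it that a patient who stops treatment for a reason other than progression goes on having tumour assessments. This is indirect support for a conflict on PFS as well.
- Safety: 10.3.1 appears to keep 90 days of reporting after the last dose. That window is shorter than 6 or 12 months.
- Analysis: 11.1 keeps the patient in ITT, and 4.4 allows no substitute.

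**Inputs**

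N = 20; planning proportion 50%, 95% confidence and precision of 22 points (synopsis, sample size). The number lost, k, is not in the documents; k = 1 or 2 is assumed. Survival p among the others is also assumed: 50%, with 30% as a second case.

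**The plan's own figure**

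n = 1.96² × 0.5 × 0.5 / 0.22² = 0.9604 / 0.0484 = 19.84, rounded up to 20. The stated sample size reproduces.

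**Unobserved part of the 12-month OS rate**

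Suppose k patients are withdrawn and censored before any death has occurred. Kaplan-Meier then reports p, the survival of the other 20 − k. The rate for all 20 lies between (20 − k)p/20, if all the lost patients died, and ((20 − k)p + k)/20, if all survived. The width is k/20.

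- p = 0.5, k = 1: 9.5/20 = 47.5% to 10.5/20 = 52.5%.
- p = 0.5, k = 2: 9/20 = 45% to 11/20 = 55%.
- p = 0.3, k = 1: 5.7/20 = 28.5% to 6.7/20 = 33.5%.
- p = 0.3, k = 2: 5.4/20 = 27% to 7.4/20 = 37%.

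Each patient therefore costs up to 5 points. A patient withdrawn after 12 months costs nothing for this endpoint.

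**Precision**

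The half-width at 50% is 1.96 × √(0.25/n): 21.9 points at n = 20, 22.5 at n = 19 and 23.1 at n = 18. This loss is small.

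**The case against.** The best reply is that the protocol can be read as a whole. On that reading 6.1.1 ends protocol treatment, while 4.3 keeps survival follow-up for everyone. Section 10.3.3 supports it, since deaths after the 90-day window are still recorded for the survival analysis, with no exception for ineligible patients. Section 10.3.1 sets reporting duties that run past permanent withdrawal, so leaving the study does not stop all data collection. This is how a careful site might act, but it is not what the 6.1.1 sentence says.

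Redaction is a fair caution. The pages after 6.1.1, the procedures in section 8 and most of 11.2 are blacked out, and a qualification or censoring rule could sit there. None is visible.

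The size can also be challenged. Section 14 provides eligibility checks and frequent database review, so such cases may be rare or caught early. Section 3.1 speaks of twenty evaluable patients, so an ineligible patient might come on top of the 20; each would then be 1/21 = 4.8% of the ITT set, which changes little. Even with two lost, the uncertainty of ±5 points is well below the sampling half-width of 21.9. These points hold, and they are why this is minor.

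A reader might go further and infer damage to the primary 4-cycle completion rate or to ORR. The documents do not support that. Any effect on the 4-cycle rate would come from stopping drug, which does not itself contradict 4.3, and it would need an ITT denominator that no visible sentence assigns to that endpoint. An effect on ORR would need withdrawal before the first 8-week scan. At the 7% to 38% response rates cited in 1.5, it would be only 7/20 = 0.35 to 38/20 = 1.9 points per patient.

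**Conclusion.** The inconsistency is real and minor. Section 6.1.1, applied literally, removes dosed ineligible patients from survival follow-up that 4.3 promises for all, while 11.1 keeps them in the analysis. The consequence is established for 12-month OS: up to 5 percentage points unobserved per patient at N = 20, with censoring that may be informative. For 6-month PFS it is probable only. A flat statement that PFS is lost would go beyond the visible text.

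This rests on four assumptions: at least one dosed patient is found ineligible; withdrawal comes before 12 months and before death; such patients are censored at withdrawal; and no blacked-out text reconciles the two sections. The direction of any bias is unknown, because it depends on which criteria were failed.

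**What to change.** Reword 6.1.1 in two parts.

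- A subject found ineligible before the first dose is not treated.
- For a subject found ineligible after dosing, the decision on further durvalumab follows 4.3 item 3. The subject stays in safety, tumour and survival follow-up, and in the ITT set as 11.1 already defines it, unless consent is withdrawn.

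The change is to wording only. Survival follow-up of all subjects is already planned; the assessment schedule is blacked out, so the visit load for tumour assessments cannot be checked. The downside is that the followed group becomes slightly more mixed, because a few patients who did not meet the entry criteria remain under observation.

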7. RESTRICTIONS DURING THE STUDY AND CONCOMITANT TREATMENT(S)

7.1 Restrictions during the study

Contraception

Females of childbearing potential who are sexually active with a non sterilised male partner must use effective contraception from screening, and must agree to continue using such precautions for at least 90 days following the last infusion of durvalumab; cessation of birth control after this point should be discussed with a responsible physician. Periodic abstinence, the rhythm method, and the withdrawal method are not acceptable methods of birth control.

- Females of childbearing potential are defined as those who are not surgically sterile (i.e., bilateral tubal ligation, bilateral oophorectomy, or complete hysterectomy) or postmenopausal (defined as 12 months with no menses without an alternative medical cause).
- Subjects must use acceptable methods of effective contraception as described in Table 2.
- Non-sterilised males who are sexually active with a female partner of childbearing potential must use acceptable methods of effective contraception (see Table 2) from Day 1 and for 90 days after receipt of the final dose of investigational product.

Table 2. Effective methods of contraception

Barrier Methods	Intrauterine Device Methods	Hormonal Methods
Male condom plus spermicide	Copper T	Implants
Cap plus spermicide	Progesterone T ^a	Hormone shot or injection
Diaphragm plus spermicide	Levonorgestrel-releasing intrauterine system (e.g., Mirena [®]) ^a	Combined pill Minipill Patch

^a This is also considered a hormonal method.

Clinical Study Protocol

Drug Substance Durvalumab (Medi4736)

Sponsor code: GECP 16/04

Version Number 4.1

Date 14th November 2018

Blood donation

As patients are HIV infected, they do not donate blood while participating in this study neither after its finalization.

Clinical Study Protocol

Drug Substance Durvalumab (Medi4736)

Sponsor code: GECP 16/04

Version Number 4.1

Date 14th November 2018

[Redacted]	[Redacted]

8. STUDY PROCEDURES

Clinical Study Protocol

Drug Substance Durvalumab (Medi4736)

Sponsor code: GECP 16/04 [REDACTED]

Version Number 4.1

Date 14th November 2018

[REDACTED]

[REDACTED]
[REDACTED]
[REDACTED]
[REDACTED]
[REDACTED]
[REDACTED]
[REDACTED]

[REDACTED]

[REDACTED]

[REDACTED]

[REDACTED]

[REDACTED]

[REDACTED]

[REDACTED]

[REDACTED]

[REDACTED]

[REDACTED]

[REDACTED]

[REDACTED]

[REDACTED]

[REDACTED]

[REDACTED]

[REDACTED]

[REDACTED]

[REDACTED]

[REDACTED]

[REDACTED]

[REDACTED]

[REDACTED]

[REDACTED]

[REDACTED]

[REDACTED]

[REDACTED]

[REDACTED]

Clinical Study Protocol

Drug Substance Durvalumab (Medi4736)

Sponsor code: GECP 16/04

Version Number 4.1

Date 14th November 2018

Clinical Study Protocol

Drug Substance Durvalumab (Medi4736)

Sponsor code: GECP 16/04

Version Number 4.1

Date 14th November 2018

Clinical Study Protocol

Drug Substance Durvalumab (Medi4736)

Sponsor code: GECP 16/04

Version Number 4.1

Date 14th November 2018

Clinical Study Protocol

Drug Substance Durvalumab (Medi4736)

Sponsor code: GECP 16/04

Version Number 4.1

Date 14th November 2018

Clinical Study Protocol

Drug Substance Durvalumab (Medi4736)

Sponsor code: GECP 16/04

Version Number 4.1

Date 14th November 2018

Clinical Study Protocol

Drug Substance Durvalumab (Medi4736)

Sponsor code: GECP 16/04

Version Number 4.1

Date 14th November 2018

Clinical Study Protocol

Drug Substance Durvalumab (Medi4736)

Sponsor code: GECP 16/04 [REDACTED]

Version Number 4.1

Date 14th November 2018

[REDACTED]

Clinical Study Protocol

Drug Substance Durvalumab (Medi4736)

Sponsor code: GECP 16/04

Version Number 4.1

Date 14th November 2018

Clinical Study Protocol

Drug Substance Durvalumab (Medi4736)

Sponsor code: GECP 16/04

Version Number 4.1

Date 14th November 2018

Clinical Study Protocol

Drug Substance Durvalumab (Medi4736)

Sponsor code: GECP 16/04

Version Number 4.1

Date 14th November 2018

The figure consists of 10 distinct groups of horizontal bars, arranged vertically. Each group contains 3 bars of increasing length from left to right. The bars are solid black and set against a white background. The groups are separated by small gaps.

Group	Bar 1	Bar 2	Bar 3
1	Short	Medium	Long
2	Medium	Long	Very Long
3	Medium	Very Long	Extremely Long
4	Very Long	Extremely Long	Max Length
5	Extremely Long	Max Length	Max Length
6	Extremely Long	Max Length	Max Length
7	Extremely Long	Max Length	Max Length
8	Extremely Long	Max Length	Max Length
9	Extremely Long	Max Length	Max Length
10	Extremely Long	Max Length	Max Length

Clinical Study Protocol

Drug Substance Durvalumab (Medi4736)

Sponsor code: GECP 16/04

Version Number 4.1

Date 14th November 2018

Clinical Study Protocol

Drug Substance Durvalumab (Medi4736)

Sponsor code: GECP 16/04

Version Number 4.1

Date 14th November 2018

A series of horizontal black bars of varying lengths, likely representing a redacted list of names or identifiers.

10. ASSESSMENT OF SAFETY

The Principal Investigator is responsible for ensuring that all staff involved in the study is familiar with the content of this section.

10.1.1 Safety Parameters

10.1.1.1 Definition of adverse events

The International Conference on Harmonization (ICH) Guideline for Good Clinical Practice (GCP) E6(R1) defines an AE as:

Any untoward medical occurrence in a patient or clinical investigation subject administered a pharmaceutical product and which does not necessarily have a causal relationship with this treatment. An AE can therefore be any unfavorable and unintended sign (including an abnormal laboratory finding), symptom, or disease temporally associated with the use of a medicinal product, whether or not considered related to the medicinal product.

An AE includes but is not limited to any clinically significant worsening of a subject's pre-existing condition. An abnormal laboratory finding (including ECG finding) that requires an action or intervention by the investigator, or a finding judged by the investigator to represent a change beyond the range of normal physiologic fluctuation, should be reported as an AE.

Adverse events may be treatment emergent (ie, occurring after initial receipt of investigational product) or non treatment emergent. A non treatment-emergent AE is any new sign or symptom,

disease, or other untoward medical event that begins after written informed consent has been obtained but before the subject has received investigational product.

Elective treatment or surgery or preplanned treatment or surgery (that was scheduled prior to the subject being enrolled into the study) for a documented pre-existing condition, that did not worsen from baseline, is not considered an AE (serious or non serious). An untoward medical event occurring during the prescheduled elective procedure or routinely scheduled treatment should be recorded as an AE or SAE.

The term AE is used to include both serious and non-serious AEs.

